7.2.2 Definitions

Evaluable for toxicity. All patients who receive at least one dose of any or all of the drugs of the investigational regimen will be evaluable for toxicity from the time of their first treatment until discontinuation or completion of the investigational therapy.

Evaluable for objective response. Only those patients who have measurable disease present at baseline, have received at least one cycle of therapy, and have had their disease re-evaluated will be considered evaluable for response. These patients will have their response classified according to the definitions stated below.

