(a) Sample size justification: The dose escalation part of the study will follow a conventional 3+3 dose escalation design according to the schema above. Up to 18 patients will be enrolled in this part anticipating that dose level 1 or 2 will be the RP2D. The number of patients to be enrolled ranges from 3 ($\geq 2/3$ DLTs in cohort 1) to 18 (enrollment of 6 patients in all cohorts). The sample size of 20 in Phase II part study is NOT determined by the statistical power but the feasibility and relative precision of estimate, e.g. standard error of the estimation is $\leq 10\%$. We will estimate the pCR of the combination to generate hypotheses for further clinical investigations. A Gehan's two-stage design will be used⁵¹ which allows for the rapid rejection of an ineffective treatment at the end of the first stage, and provides an estimation of the success rate with a given precision, at the end of the second stage. The study will enroll 10 patients first. If no patient has pCR or downstaging, it is unlikely ($p=0.1074$) that 0/10 responses would occur if the true response rate were $>20\%$ and the phase II portion will be closed. If at least one patient has pCR or downstaging, an additional 10 patients will be treated (total of 20). With an accrual of 20 patients to phase II portion of the study, estimated two-sided 95% confidence intervals (CI) would be 1.2%-31.7%, 5.7% -43.6% and 11.8%-54.3% if pCR is 10%, 20% or 30% respectively. The confidence intervals are calculated using the exact method Clopper-Pearson intervals⁵⁴. Final analysis will include all patients enrolled in the trial.

(b) Analytic plan for primary objective: The rate of adverse events will be estimated at the end of the study along with two-sided 95% exact CIs (Clopper-Pearson intervals).

(c) Analytic plan for secondary objectives:

1. pCR or downstaging rate will be estimated along with two-sided 95% CIs with the exact method of Clopper-Pearson intervals.
2. We will use descriptive statistics (mean, median, geometric mean, coefficient of variation, and 95% confidence intervals) and graphical displays to evaluate the pharmacokinetic parameters of the TRC105 and everolimus.
3. We will use descriptive statistics (mean, median, geometric mean, coefficient of variation, and 95% confidence intervals) and graphical displays to analyze the changes in markers of proliferation and angiogenesis with the investigational treatment.

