Adverse events. The addition of everolimus to letrozole has been associated with a higher rate of dose reductions or interruptions due to adverse events (52.9%) as well as discontinuations (18.8%) compared with letrozole alone (7.6% and 9.1%, respectively) in the neoadjuvant setting⁴. Grade 1 and 2 adverse events were also more frequent in the combination arm (89.8% vs. 63.6% in the letrozole alone arm)⁴. The most frequent adverse events seen in higher frequency in the combination arm as compared to the letrozole alone group include stomatitis (36.5% vs. 6.1%), rash (20.4% vs. 7.6%), asthenia (17.5% vs. 9.8%), fatigue (12.4% vs. 4.5%), anorexia (12.4% vs. 3.8%), headache (10.9% vs. 5.3%), pruritus (13.1% vs. none), dyspnea (7.3% vs. 1.5%), pneumonitis (2.9% vs. none). Laboratory abnormalities seen in higher frequency in the combination arm as compared with the control arm include hypercholesterolemia (16.1% vs. 6.1%), thrombocytopenia (18.2% vs. 0.8%), hyperglycemia (13.1% vs. 3%), increased ALT (11.7% vs. 3.8%), anemia (11.7% vs 0.8%), and neutropenia (9.5% vs. 1.5%).

Grade 3 and 4 adverse events were also more frequent in the combination arm (22.6%) as opposed to the letrozole alone arm (3.8%). Stomatitis (2.2%), fatigue (1.5%), and pneumonitis (2.2%) were the most frequent grade 3 and 4 adverse events seen in more than 1 patients (n=137) associated with the addition of everolimus, while hyperglycemia (5.1%), increased ALT (1.5%), hypokalemia (1.5%), thrombocytopenia (1.5%) constituted the most frequent biochemical grade 3 and 4 adverse events. Serious adverse events associated with everolimus occurred in 7/137 patients: pneumonitis in three patients; pneumonia and mouth ulcers/stomatitis each in two patients; and dyspnea, neutropenia, and thrombocytopenia in one patient each. All three patient cases of pneumonitis resolved within 15 days of everolimus discontinuation. Among the placebo-treated patients, there was one serious adverse event of myocardial ischemia⁴.

Overall, safety data available from completed, controlled and uncontrolled studies indicate that everolimus is generally well tolerated at weekly or daily dose schedules. The safety profile is characterized by manageable adverse events (AEs). These AEs are generally reversible and non-cumulative.

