7.2.4 Evaluation of Response Reporting

Studies in the neoadjuvant setting in breast cancer have used various endpoints in the assessment of response including rates of pCR^{12,59,60,119}, radiographic response¹, and clinical response^{4,14,17}. Although these endpoints may have their limitations, the rates of pCR is the outcome measure least subject to serious errors of measurement and interpretation. All three outcome measures will be recorded and reported. The following definitions will be used:

- a. **Clinical response:** the target lesion will be clinically assessed and measured using calipers on each visit. At least 2 dimensions will be measured and recorded. The maximum reduction in the maximum dimension of the tumor from baseline will be recorded as the best clinical response.
- b. **Radiographic response:** the target lesion(s) will be measured and recorded at least in 2 dimensions on mammograms, breast ultrasound, and MRI. RECIST will be used to assess the best radiographic response (see below 7.2.5 **Methods for Evaluation of Measurable Disease**).
- c. **Pathologic response:** the 2-dimensional size of the surgically excised residual tumor will be measured and compared to the radiographic size of the tumor at baseline. The maximum dimension will be used for comparison.

Definition of pathologic complete remission (pCR): the definition adopted by the Center for Drug Evaluation and Research of the FDA¹⁰⁴ will be used to define and report pCRs. According to the Center for Drug Evaluation and Research of the FDA, a pCR is defined as the absence of any residual invasive cancer on hematoxylin and eosin evaluation of the resected breast specimen and all sampled ipsilateral lymph nodes following completion of neoadjuvant systemic therapy (i.e., ypT0 ypN0 in the current AJCC staging system)¹⁰⁴. For this protocol, near pCR will be considered if the breast residual disease is less or equal to 0.5 cm.

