10.2 Statistical Analysis

The primary analysis is of safety and will include any patients who receive at least one dose of the investigational regimen. The rate of adverse events will be estimated at the end of the study along with two-sided 95% exact CIs (Clopper-Pearson intervals). At the completion of the study, the secondary endpoint of pCR or downstaging rate will be estimated along with two-sided 95% CIs with the exact method of Clopper-Pearson intervals. Secondary endpoint analysis will be descriptive. Mean, median, geometric mean, range and coefficient of variation will be used to describe continuous demographic variables. Frequency and proportion will be used to describe categorical variables.

We will use descriptive statistics (mean, median, geometric mean, coefficient of variation, and 95% confidence intervals) and graphical displays (mean concentration-time graphs, scatter plots, box plots or spaghetti plots) to evaluate the pharmacokinetic parameters of the TRC105 and everolimus. We will use descriptive statistics (mean, median, geometric mean, coefficient of variation, and 95% confidence intervals) and graphical displays (scatter plots, box plots, plots of PD parameters against PK data) to analyze the changes in markers of proliferation and angiogenesis with the investigational treatment.

Exploratory analysis will be conducted on the correlations between clinical outcomes and pharmacodynamic biomarkers or translation profiles. Translational profiles will be analyzed between responders and non-responders and the differences between responders and non-responders will be presented in scatter plots along with corresponding 95% CI. Quartile normalization and logarithmic transformation will be conducted before analysis. Logistic regression analysis will be used to predict response with translational profiles or biomarkers with or without adjustment for covariates, e.g. age. Multivariate Cox proportional hazards model will be used to identify a set of biomarkers for prediction of response. Odds ratios with 95% CIs will be calculated for each significant biomarker in terms of predicting response. However, it is recognized that sample size may be too small for such analyses and these analyses are conducted only to generate hypotheses that will require further validation.

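### The efficacy denominator is written two ways and never settled: Section 7.2.2 drops patients who stop within cycle 1, the synopsis counts everyone enrolled, and Section 10.2 names no set for pCR/downstaging.

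*Combined protocol and SAP*

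**What the plan says.** Three places bear on who is counted for efficacy.

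- **Section 7.2.2**, under the label "Evaluable for objective response", provides that only patients who show measurable disease at baseline, "have received at least one cycle of therapy, and have had their disease re-evaluated will be considered evaluable for response". It continues: "These patients will have their response classified according to the definitions stated below". The definitions that follow, in Section 7.2.4, cover clinical, radiographic and pathologic response, including pCR, and that section adds: "All three outcome measures will be recorded and reported".
- **Synopsis, Statistical Methods (a)**, closes its sample-size paragraph with: "Final analysis will include all patients enrolled in the trial". It names no endpoint and no study part. Section 10.1 repeats most of that paragraph but not this sentence.
- **Section 10.2** defines the safety population as anyone given at least one dose. For efficacy it says only that "the secondary endpoint of pCR or downstaging rate will be estimated along with two-sided 95% CIs", by the Clopper-Pearson method. No denominator is given.

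The design text in Sections 4.2 and 10.1 speaks of enrolling 10 patients, then treating 10 more, for a total of 20. Section 4.1.3 replaces phase I patients who withdraw before completing cycle 1 for reasons other than DLT. No replacement or missing-outcome rule is written for phase II.

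**The concern.** Receiving a cycle and being re-evaluated both happen after treatment starts, so the 7.2.2 set is selected on events that the regimen can influence. Loss within cycle 1 is foreseeable here. Section 5.2.3.1 says that infusion reactions usually come with the initial TRC105 dose, and Table 5-10 takes a patient with a grade 4 reaction off study. Section 5.3 takes a patient off study if treatment cannot be resumed within 7 days. If such patients are left out, poor early tolerability shrinks the denominator, and the regimen can look more active than it was among those who started it.

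The synopsis sentence has the opposite problem. Section 4.3 expects 26 to 38 patients in all, and 38 − 20 = 18 of them may belong to phase I. Section 10.1 reaches 18 by filling three cohorts of 6. If one of those cohorts is the RP2D, up to 12 patients were treated at another dose level. Counting them makes the estimate something other than the response rate at the RP2D.

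For pCR and downstaging, the efficacy endpoints in Section 10, neither rule is clearly adopted. The choice could then be made after the data are seen, in a sample where each patient is worth 5 percentage points (1/20).

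**Working it through.** **1. Reproduce the plan's figures (Section 10.1).** The Clopper-Pearson limits for x responders out of n are the 2.5% quantile of Beta(x, n − x + 1) and the 97.5% quantile of Beta(x + 1, n − x). With n = 20:

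| Responders | Plan | Recomputed |
|---|---|---|
| 2 (10%) | 1.2 to 31.7% | 1.23 to 31.70% |
| 4 (20%) | 5.7 to 43.6% | 5.73 to 43.66% |
| 6 (30%) | 11.8 to 54.3% | 11.89 to 54.28% |

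These agree, apart from two limits that the plan truncates rather than rounds. The stage 1 figure also reproduces: 0.8^10 = 0.1074. The planned precision therefore rests on a denominator of 20.

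**2. Effect of the 7.2.2 restriction.** Hold the responders x fixed and remove k patients, all non-responders. The rate changes from x/20 to x/(20 − k), so it is multiplied by 20/(20 − k). The documents do not give k. I assume a range of 0 to 4 of 20. At the 20% planning rate (x = 4):

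| k | Factor | Rate | 95% CI |
|---|---|---|---|
| 0 | 1.00 | 4/20 = 20.0% | 5.73 to 43.66% |
| 1 | 1.05 | 4/19 = 21.1% | 6.05 to 45.57% |
| 2 | 1.11 | 4/18 = 22.2% | 6.41 to 47.64% |
| 3 | 1.18 | 4/17 = 23.5% | 6.81 to 49.90% |
| 4 | 1.25 | 4/16 = 25.0% | 7.27 to 52.38% |

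At the other planning rates with k = 4, 2/20 = 10.0% becomes 2/16 = 12.5%, and 6/20 = 30.0% becomes 6/16 = 37.5%. The planning rates in Section 10.1 are for pCR. They serve here as a worked example, and the factor is the same for clinical or radiographic response.

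**3. Direction.** If k = 2 and one of the two excluded patients was a responder, the rate falls to 3/18 = 16.7% (3.58 to 41.42%). Upward bias needs the excluded patients to respond less often than those kept. That is likely for patients who stop within cycle 1, but it does not follow from the text.

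**The case against.** The strongest reply is that this is an omission in Section 10.2 rather than a biased analysis on paper. Much of it stands, and it rules out several stronger readings that a reader might infer.

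- **That 7.2.2 governs pCR and downstaging.** Its label is objective response, within the RECIST text. The cross-reference to later definitions, which include pathologic response, makes the wider reading arguable, but no passage states it. Section 10.2 also specifies no rate or interval for clinical or radiographic response.
- **That patients must complete a cycle, or that progression generally removes them.** The text says received. The first scheduled ultrasound is at week 4 (Section 5.4.2), and progression found there is itself a re-evaluation, so the patient stays in. Section 5.4.3 also requires imaging at early termination. That imaging does not help a patient who stops within cycle 1, because the one-cycle condition still fails.
- **That patients taken off study have no pathology.** Section 4.7 sends patients with progression, or with stable disease after four cycles, to surgery or chemotherapy. Some will have a surgical specimen. What is missing is a rule for counting it.
- **That the 18.8% discontinuation figure in Section 5.2.2 measures the loss.** It covers the whole treatment period of an earlier letrozole-everolimus study. Patients who stop later, after a re-evaluation, remain in the 7.2.2 set.
- **That the stage 1 rule is altered.** It says 10 enrolled and counts responders, so removing non-responders from those 10 cannot change whether the count is zero.

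The endpoint is also secondary and descriptive, the 20 patients are not powered, and the safety population is clearly defined. The synopsis sentence follows the phase II interval text and may have been meant for phase II only.

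One thing is left unanswered. A written rule does condition a response denominator on post-treatment events, it conflicts with another written rule, and the statistical section does not choose between them.

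**Conclusion.** The point holds in a limited form. For clinical and radiographic response, Section 7.2.2 excludes patients who stop within cycle 1 or are never re-evaluated, while the synopsis literally includes everyone at every dose level. For pCR/downstaging no denominator is written, and nothing says how a patient without protocol surgery is counted.

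The size is modest: a factor of 1.05 to 1.25 for one to four of 20 lost, or 1.1 to 5.0 points at a 20% rate, with heavily overlapping intervals. This rests on two assumptions: that the loss lies between 0 and 4, for which the documents give no first-cycle rate, and that the excluded patients are non-responders. The primary safety analysis is unaffected. The inconsistency should be corrected before any efficacy data are tabulated.

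**What to change.** Reconcile the synopsis, Section 7.2.2 and Section 10.2 as follows.

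- Define one primary efficacy set, for pCR/downstaging and for clinical and radiographic response: all phase II patients who start treatment at the RP2D. This matches the 10 and 20 patients in Section 10.1.
- Count no surgery, missing pathology or no re-evaluation as non-response. State in the same place how pathology obtained after off-protocol chemotherapy is classified.
- Keep the 7.2.2 evaluable set as a named sensitivity analysis.
- Replace the synopsis sentence with the same definition, and report response in phase I patients separately by dose level.

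This changes wording only and needs no extra patients, visits or time. The one cost is that the reported response rate may be slightly lower than on the evaluable set.

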7.2.3 Disease Parameters

Measurable disease. Measurable lesions are defined as those that can be accurately measured in at least one dimension (longest diameter to be recorded) as ≥ 20 mm with conventional techniques (mammogram, breast ultrasound, exceptionally MRI). All tumor measurements must be recorded in millimeters (or decimal fractions of centimeters). Note: Tumor lesions that are situated in a previously irradiated area should not be considered measurable.

Non-measurable disease. All other lesions (or sites of disease), including small lesions (longest diameter < 20 mm with conventional techniques), are considered non-measurable disease. For this protocol it will be satellite lesions in the affected breast.

Target lesions (not applicable for this trial). All measurable lesions up to a maximum of 5 lesions per organ and 10 lesions in total, representative of breast(s) involved, should be identified as **target lesions** and recorded and measured at baseline. Target lesions should be selected on the basis of their size (lesions with the longest diameter) and their suitability for accurate repeated measurements (either by imaging techniques or clinically). A sum of the longest diameter (LD) for all target lesions will be calculated and reported as the baseline sum LD. The baseline sum LD will be used as reference by which to characterize the objective tumor response.

Non-target lesions (not applicable for this trial). All other lesions including any measurable lesions over and above the 10 target lesions should be identified as **non-target lesions** and should also be recorded at baseline. Measurements of these lesions are not required, but the presence or absence of each should be noted throughout follow-up.

7.2.4 Evaluation of Response Reporting

Studies in the neoadjuvant setting in breast cancer have used various endpoints in the assessment of response including rates of pCR^{12,59,60,119}, radiographic response¹, and clinical response^{4,14,17}. Although these endpoints may have their limitations, the rates of pCR is the outcome measure least subject to serious errors of measurement and interpretation. All three outcome measures will be recorded and reported. The following definitions will be used:

- a. **Clinical response:** the target lesion will be clinically assessed and measured using calipers on each visit. At least 2 dimensions will be measured and recorded. The maximum reduction in the maximum dimension of the tumor from baseline will be recorded as the best clinical response.
- b. **Radiographic response:** the target lesion(s) will be measured and recorded at least in 2 dimensions on mammograms, breast ultrasound, and MRI. RECIST will be used to assess the best radiographic response (see below 7.2.5 **Methods for Evaluation of Measurable Disease**).
- c. **Pathologic response:** the 2-dimensional size of the surgically excised residual tumor will be measured and compared to the radiographic size of the tumor at baseline. The maximum dimension will be used for comparison.

Definition of pathologic complete remission (pCR): the definition adopted by the Center for Drug Evaluation and Research of the FDA¹⁰⁴ will be used to define and report pCRs. According to the Center for Drug Evaluation and Research of the FDA, a pCR is defined as the absence of any residual invasive cancer on hematoxylin and eosin evaluation of the resected breast specimen and all sampled ipsilateral lymph nodes following completion of neoadjuvant systemic therapy (i.e., ypT0 ypN0 in the current AJCC staging system)¹⁰⁴. For this protocol, near pCR will be considered if the breast residual disease is less or equal to 0.5 cm.

7.2.5 Methods for Evaluation of Measurable Disease

All measurements should be taken and recorded in metric notation using a ruler or calipers. All baseline evaluations should be performed as closely as possible to the beginning of treatment and never more than 4 weeks before the beginning of the treatment.

The same method of assessment and the same technique should be used to characterize each identified and reported lesion at baseline and during follow-up. Evaluation by clinical examination will always be complemented by imaging evaluation. See **Appendix C** for guidelines issued by the American College of Radiology for imaging studies of the breast. In cases of discrepancy between clinical and radiographic evaluation by >1 cm, a complementary imaging technique (breast ultrasound when the mammograms are inconclusive and breast MRI when both mammograms and breast ultrasound are inconclusive) will be used for the initial and subsequent assessments of the target lesion(s).

7.2.5.1 Clinical Assessments

Target lesion(s) in the breast or target ipsilateral lymph nodes will be measured using calipers and the size in two dimensions will be recorded on each clinical visit.

7.2.5.2 Mammography

Standard diagnostic mammograms will be used to identify and follow the target lesion(s) during the course of the protocol treatment. All mammograms will be obtained at the Kirklin Clinic which meets the requirements set forth by the Mammography Quality Standards Act (MQSA) final rule published by the Federal Drug Administration (FDA).

Technical considerations of diagnostic mammography (The American College of Radiology Practice Guideline for the Performance of Screening and Diagnostic Mammography, <http://www.acr.org/~media/3484ca30845348359bad4684779d492d.pdf>):

1. A diagnostic mammogram will include mediolateral oblique (MLO), craniocaudal (CC), and/or supplemental views to evaluate an area of clinical or radiographic concern.
2. Supplemental mammographic views might include spot compression, spot compression with magnification, tangential views, or other special views.
3. When selecting a view, the proximity of the area of concern to the image receptor should be considered.
4. Diagnostic mammography should be performed under the immediate supervision of the interpreting physician.

